Pain-related Measures. At the beginning of each module, the Veteran will be asked to rate their current level of pain using a 11-item pain intensity scale. In addition, the following two assessments will be provided pre- and post- intervention: *Pain Outcomes Questionnaire – Short Form (POO-SF)*⁴⁷ is a 20-item inventory that assesses patient's ability to engage in functional activities related to daily living that may be impacted by pain interference; and *The Chronic Pain Acceptance Questionnaire (CPAQ)*⁴⁸ is 20-item survey measuring recognition of pain as not negating the ability to live valued life. We will also assess pain interference, again using the *Brief Pain Inventory*. This battery of pain -related measures will take approximately 25 minutes.

Mental Health Co-Morbidity Measures. To assess for important psychological co-morbidities in chronic pain treatment, we will administer the 9 – item Patient Health Questionnaire-9 (PHQ-9)⁶¹ to assess for depressive symptoms, and 20-item PTSD Checklist-5 (PCL-5).⁴¹ These surveys will take approximately 7 minutes.

Valued Living. *The Chronic Pain Values Inventory (CPVI)* is a 12-item self-report measure of the extent to which the patient is living in accordance with their values in areas such as work, health, and family, which is related to lower perceived disability and pain-related anxiety, as well as greater reported patient functioning even in the context of high levels of pain.⁶² This survey will take approximately 3 minutes.

Behavioral Avoidance. The *Multidimensional Experiential Avoidance Questionnaire (MEAQ)* is a 62-item self-report measure of experiential avoidance, including subscales on Behavioral Avoidance, Distress Aversion, Procrastination, Distraction & Suppression, Repression & Denial, and Distress Endurance.⁵⁰ This survey will take approximately 12 minutes.

Patient Satisfaction with Treatment: *Client Satisfaction Questionnaire-8. (CSQ-8)*⁵¹ This 8-item scale measures global satisfaction, perceived quality, and effectiveness of the proposed mental health treatment. This scale has been used in mental health and other health centers, and has acceptable internal consistency ($\alpha=.83-.93$). This survey will take approximately 2 minutes.

Therapeutic Alliance: *Working Alliance Inventory-Short Form (WAI-S)*⁵² This 11-item scale will be administered to obtain both an early and a late alliance assessment between the Veterans and VACT-

CP virtual ECA therapist that will walk patients through the treatment. It has acceptable internal consistency (Cronbach's $\alpha=.83\text{-.98}$) and predictive validity related to therapy outcome. This scale will take approximately 2 minutes.

a Storage

Data collected online via Qualtrics will initially be stored on the Qualtrics platform. This platform is HIPAA compliant and has been approved by the VA FedRAMP's process for data collection and storage. After collection is complete, this data will be transferred from the Qualtrics platform directly into password protected files on a VA sharepoint site:

<https://vaww.visn1.portal.va.gov/sites/mirecc/vactcp/> that is designated and accessible for this study only.

b Collection of PHI

Data collected online will be stored on the FedRAMP approved, HIPAA compliant platform, both on the Qualtrics platform and when transferred to a VA platform. Only members of the approved research staff will have access to this data.

3.5 Analysis Plan

Phase One:

Primary analyses. We will gather feedback from semi-structured interviews on system interest, concerns, issues, and suggestions for improvement to VACT-CP so that we are better suited to move forward with completed development and future pilot testing at VA Bedford. Preliminary analyses will include assessment of qualitative data for transcription errors. As only 10 - 12 subjects will participate in quantitative surveying on workplace history and general demographics, only aggregated information will be reported.

Qualitative Interview Analysis: The audio recordings and notes made by [name] during the qualitative interview will be transcribed and analyzed using Excel or NVivo software available through the Bedford VAMC. A modified consensual qualitative research (CQR) approach will be utilized to code the transcribed audio, which [name] has been trained in and utilized in past peer-reviewed publications. CQR can be particularly useful in allowing for a team of coders to identify themes arising in both structured and more open-ended interview moments. [name] will develop an initial codebook for using in coding based on the key activities and questions in the semi-structured interview protocol.

[name] and another research staff member will then employ the codebook in identifying usability-themes within the audio, with an additional research staff identified to act as a code auditor. According to CQR, the following processes occur to allow for depth and breadth in describing the shared experiences of participants: (b) two coders utilize the initial codebook throughout the data analysis process to foster multiple perspectives, and revise the codebook as needed; (c) consensus is researched between coders about the meaning of the data; (d) at least one auditor must check the work of the

primary team of judges and minimize potential bias; and (e) domains and themes are reported in terms of the frequency of arising themes.

Themes will then be categorized according to the following CQR groupings: *general* (include all or all but one of the cases), *typical* (include more than half of the cases up to the cutoff for *general*), and *variant* (at least two cases up to the cutoff for *typical*). Specifically, the themes generated by this qualitative data will be used to identify potential user issues, concerns, intervention opportunities, and general trends and categories of provider's perceptions' of the VACT-CP system. Using this method, we will classify all general comments regarding usability as necessary to include in iterative development and refinement, while *variant* and *typical* will be discussed within the research group to decide upon potential ways to incorporate this feedback into intervention refinement. Research staff will then summarize suggested changes, obtain input from the full research team, then meet with the VACT-CP programmers to implement potential changes. Results will be published to inform other researchers about development and implementation findings related to referrals to online behavioral interventions for pain, preferred user interfaces, provider interest, and perceptions of behavioral intervention content and needs.

Phase Two:

Similar to Phase One of the research, the video recordings and notes made by [name] during the qualitative portion of user testing will be transcribed and analyzed using coding software options (e.g., NVIVO or Excel) available through the Bedford VAMC. A modified consensual qualitative research (CQR) approach will be utilized to code the transcribed videos, which [name] has been trained in and utilized in past peer-reviewed publications. CQR can be particularly useful in allowing for a team of coders to identify themes arising in both structured and more open-ended interview moments. [name] will develop an initial codebook for using in coding based on the key activities and questions in the user-testing protocol. [name] and the research associate will then employ the codebook in identifying usability-themes within the videos, with an additional research staff identified to act as a code auditor. According to CQR, the following processes occur to allow for depth and breadth in describing the shared experiences of participants: (a) two coders utilize the initial codebook throughout the data analysis process to foster multiple perspectives; (b) consensus is researched between coders about the meaning of the data; (c) at least one auditor must check the work of the primary team of judges and minimize potential bias; and (d) domains and themes are reported in terms of the frequency of arising themes.

Themes will then be categorized according to the following CQR groupings: *general* (include all or all but one of the cases), *typical* (include more than half of the cases up to the cutoff for *general*), and *variant* (at least two cases up to the cutoff for *typical*). Specifically, the themes generated by this qualitative data will be used to identify user performance measures, errors, and difficulties, and tasks that do not meet acceptable criteria, and general trends and categories of users' behavior, such as how well users can complete an assigned task on the VACT-CP system and where they are encountering problems. Using this method, we will classify all general comments regarding usability as necessary to include in iterative development, while *variant* and *typical* will be discussed within the research group to decide upon potential ways to incorporate this feedback into intervention refinement.

In addition, Veterans will complete a series of brief usability questionnaires following user testing and the qualitative interview. Usability Survey and SUS data will be input into an excel spreadsheet and reported descriptively using SPSS software, and used to describe Veteran's general perceptions and opinions of the technology's usability, both within the controlled testing setting and for future use within their home. This feedback will then be triangulated with qualitative data and used to iteratively refine the VACT-CP program between the three waves of user testing. We will complete this process with 4-5 Veterans per round; [name] will then summarize suggested changes, obtain input from the full mentoring team, then meet with website staff to implement potential changes.

Phase 3:

Data management procedures described for Phase 2 will be used in Phase 3. The PI will direct data management and analyses in consultation with CDA-2 mentors Drs. [name], [name], and [name].

Power analysis. Consistent with the recommended stage model for development of behavioral therapies, the aim of this stage I Pilot Study is to inform future treatment development and evaluation plans. Given that prior investigations of ACT have reported effect sizes within the large to medium range, we expect VACT-CP will also produce a medium treatment effect. In order to have .80 power to detect differences at a two-tailed alpha level of .05, a medium effect would require n=125. This is beyond the scope of a CDA-2 award, and is more appropriate for a stage II trial. A total sample size of 40 is feasible (n=20 per group) and consistent with Rounsville et al.'s⁵³ recommendation of 15 to 30 subjects per condition for stage I behavioral treatment development.

[Primary Analyses and Hypotheses, Aim 3a:

Hypothesis One: Given prior usability research, we predict that both perceived ease of use and perceived usefulness will be strongly correlated with behavioral intention and actual use of VACT-CP.

Hypothesis Two: We predict that higher behavioral intention, perceived system usability, and intrinsic motivation to use VACT-CP will correlate positively with actual use (number of modules completed).

We will focus on usability of the VACT-CP system in home setting to test Aim 3a. Usability will be primarily measured via the Usability Survey Subscales for antecedent user features (e.g., health care need). The Usability Survey Subscales and System Usability survey will assess for acceptability features at both pre- and post-intervention (e.g., perceived ease of use, perceived usefulness, intrinsic motivation, and system usability) We will then assess if these usability factors relate to intended and actual use statistically using bivariate correlations.

To address Aim 3a, we will first compile descriptive statistics for each of the ITAM measures, determine Cronbach's alphas for each of the ITAM component subscales, and compute bivariate Pearson's correlations to assess relationships between acceptability, antecedent and intention and actual use factors of the ITAM. Next, where we have sufficient data from participants receiving the same intervention we will use multiple linear regression models for VACT-CP use to model which acceptability features (intrinsic motivation, perceived ease of use, perceived usefulness, system usability) are most strongly related to behavioral intention to use modules and with actual use.

Additional data will be provided by the semi-structured qualitative interviews and tracking of any calls to research staff with concerns. Analysis of post-intervention interviews will be done using notes taken by one of the team members during the exit interview; interviews will also be audiotaped for later use if needed. [name] and research staff will apply CRQ qualitative analytic techniques (see Phase 2 Data Analysis plan) to these data (e.g., coding for and extracting major themes) to assess both barriers and facilitators to use of the VACT-CP system, and individual demographic user factors that impact use. Finally, we will behaviorally assess feasibility by measuring the proportion of individuals who successfully complete the 8 week trial with at least 5 completed modules, which would be 71% of the program completed and slightly above the mean number for percentage of completed sessions found in previous online behavioral interventions.⁵⁸

Secondary Analyses, Aim 3b.

Hypothesis One: We will observe increases in the means scores on pain acceptance, functioning, behavioral avoidance, mental-health symptoms (PTSD and depression), and values-oriented living given past ACT-based chronic pain interventions research for VACT-CP participants.

Hypothesis Two: We predict that there will be small- to no-change in means on pain levels, given research suggesting that behavioral intentions do not change pain levels overall.⁵⁸

To address Aim 3b, we will describe the outcome variable scores from pre- to post-intervention using subjective pain-related outcomes and quality of life measures. Because we have proposed a rolling design where changes in the delivery of VACT-CP intervention can be made with each wave of participants, the number of participants given the same version of the self-management program may be too few to test these outcome effects at a conventional level of significance. We will thus describe differences by reporting means and standard deviations pre- and post-levels of outcomes (pain acceptance, pain levels, pain functioning, behavioral avoidance, mental-health comorbidities, and values-oriented living). We will also use mental health measures to describe our sample and explore if groups are equivalent based on these measures.

Based on the intent-to-treat principle, all subjects enrolled in the pilot study treatment will be included in analyses, and the PI will conduct preliminarily analyses and descriptively report on the pilot RCT outcomes of the VACT-CP intervention in order to inform further refinements to VACT-CP. Additional outcomes of interest, including working alliance and treatment satisfaction will also be reported and described in terms of their means and standard deviations. Due to imprecise estimations due to small sample size, we will not report estimates of effect sizes as a specific hypothesis or aim; however, we will explore and report on descriptives (means, standard deviations) between pre- and post-scores.

Secondary Analyses, Aim 3c.

To evaluate the feasibility of recruiting the necessary sample for a larger randomized controlled trial by determining the effect size for future studies. Leon and colleagues⁵⁹ point out that a pilot study does not necessarily provide the meaningful effect size estimates necessary for planning subsequent larger studies due to the imprecision inherent in data from small samples. However, it will provide feasibility and acceptability data.

Hypothesis One: We anticipate acceptable exclusion/inclusion criteria for recruitment, acceptable retention rates for randomization, and equivalent retention rates within each condition.

Hypothesis Two: We anticipate that Veterans within the VACT-CP condition will report higher rates of treatment satisfaction compared to the wait-list control.

We will specifically utilize this information to design the large efficacy trial for the Merit Review application. For example, if recruitment rates are low, we will plan to add another VA site. If a higher-than-acceptable number of Veterans are excluded due to exclusion criteria, we will re-examine whether that eligibility criterion is necessary. If retention rates are lower than acceptable, the PI and research team will discuss how to retain more Veterans before moving to the efficacy trial, and build retention rates into your sample size calculation. For the purposes of a future Merit Review application sample size estimation, we will calculate sample size requirements results of previous adequately-powered chronic-pain behavioral interventions, and we will secondarily consider the impact of our intervention on reported pain-acceptance and functional improvement in this small pilot RCT.]

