Phase Three: Following recruitment, a research associate not otherwise involved in the study will screen participants prior to enrollment. Veterans will be randomized in a 1:1 ratio, with a research staff member utilizing and keeping the schedule. Veterans randomized to VACT-CP (and online website that includes 7 online-module based weekly sessions of treatment) via personal computer or provided laptop at the Bedford VAMC. Veterans in the waitlist control will be provided with a list of common pain resources at the Bedford VAMC. The VACT-CP program will be housed on a secure web server through Northeastern University, with no Veteran private health information collected by the system. Veterans in both conditions will complete the assessment battery (see Table 2 for specific schedule) at baseline, either in-person or remotely (via a phone call or online using the VA-approved Qualtrics survey platform) depending on the participant’s preference. In addition, the full battery of primary outcomes and process measures will be taken at mid-point of the intervention phase (3 weeks) and at the end, immediately following the treatment (7 weeks). Veterans will be tracked in terms of their post-referral treatment engagement (e.g., enrolling in any of the pain-resource options on the handout). In addition, a research associate will call the Veteran at weeks 3 and 6 and conduct a brief safety assessment with Veterans assess for potential suicidality, usability issues, and participant health and well-being.

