(SCID-5) to assess for potential psychosis, substance use disorders, or clinically-significant suicidality. Eligible subjects will then complete self-report measures. Participants with additional, co-morbid pain diagnoses will not be excluded. Data will be collected at baseline, the study midpoint (approximately 3 weeks), end of treatment/7 weeks, and at the one-month follow-up period. Self-report baseline and post-baseline assessments will be administered either in-person or online by Qualtrics, a VA-approved platform and vendor. Length of time for assessments will take approximately 2 hours for baseline assessments, 1.5 hours for the mid-point survey, approximately 2 hours for the 7 week/post-intervention surveys, as well as approximately 1 hour for the 1 month follow-up surveys. See Table 2 for the measurement schedule:

Table 2: Measurement Schedule for Phase 3

MEASURE	BASELINE	MIDPOINT	INTERVENTION END /7 WEEKS	1-MONTH FOLLOW- UP
Demographics	X			
MEAQ	x		x	x
CPVI	x	x	x	x
PHQ-9	x	x	x	x
VR-36	x	x	x	x
POQ-SF	x	x	x	x
SCID-5	x			
BPI	x			
CPAQ	x	x	x	x
Usability survey*			x	
SUS*			x	
WAIS-S*			x	
CSQ-8*			x	
Qualitative Interview			x	

*will only be assessed in invention group

Demographics, functional health, and pain measures.

Demographic measures will include age, gender, race and ethnicity, and education. We will also include questions related to medications currently being used for the management of physical or psychological conditions, self-reported using a single-item listing diagnoses, and at baseline and 7 weeks conduct a CPRS record review for such information. These measures will take approximately 10 minutes.

Feasibility and

Acceptability Measures: Feasibility outcomes will include recorded information on recruitment rates, retention rates within each condition, measure completion rates, how often Veterans access the website, and any reported problems with the website. This information will be collected by the research team.

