Quality of Life. *The Veteran's RAND 36 Item Health Survey (VR-36)*⁴³ is 36-item measure of health including physical functioning, role limitations due to physical problems, bodily pain, general health perceptions, vitality, social functioning, role limitations due to emotional problems, and mental health. It is often summarized into (physical functioning components and mental functioning components, and is one of the most widely utilized and valid measures of physical and psychological well-being. This survey will take approximately 15 minutes.

Usability Survey. The usability survey items were adapted from an existing set of usability questions to make the questions specific to the VACT-CP online treatment. The items form 2-4 item subscales that will be used to address relationships between elements of our modified Integrated Technology Acceptance Model.³⁵ We will assess antecedent conditions that are proposed to influence HIT

acceptance and use, including satisfaction with medical care, preferences for seeking information, health care needs, internet dependence, and health care knowledge. In addition, we will assess intrinsic motivation, perceived ease of use, and perceived usefulness of each HIT. Prior versions of the subscales have shown good internal consistency reliability for each subscale (Cronbach's alphas > 0.7 for all but information seeking preference which was 0.60). The usability survey should take the average user about 5-7 minutes.

System Usability Scale (SUS; Brooke, 1996) a 10-item measure, scored on a 5-point Likert scale, that assesses human-computer interaction. A SUS score above 58 is regarded as above average, and a SUS score above 80 is regarded as high and a score above which participants are likely to recommend the product to friends. The SUS generates a subjective evaluation score using a globally accepted scale and to understand if the system in its current form is sufficiently usable.⁴⁴ This survey will take approximately 3 minutes.

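### Primary Aim 3a: the analysis text takes the usability scales before and after the intervention, but Table 2 schedules them once, at week 7

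*Combined protocol and SAP*

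**What the plan says.** Section 3.5 (Analysis Plan, Phase 3) labels Aim 3a the primary analysis. On timing it states: "The Usability Survey Subscales and System Usability survey will assess for acceptability features at both pre- and post-intervention". The features it lists are ease of use, usefulness, intrinsic motivation and system usability. These scores are then to be correlated with intended and actual use, and Hypothesis Two defines actual use as the number of modules completed.

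The schedule is in section 3.4 (Data Collection, Phase 3), which directs the reader: "See Table 2 for the measurement schedule". Section 3.3 (Study Procedures, Phase Three) does the same for the assessment battery: "see Table 2 for specific schedule". In Table 2 the Usability Survey and SUS rows each carry one mark, in the column for intervention end/7 weeks. The footnote to these rows says that they "will only be assessed in invention group" (a slip for intervention).

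The instrument description in section 3.4 covers two kinds of subscale. On the first it says: "We will assess antecedent conditions that are proposed to influence HIT", going on to acceptance and use. On the second: "In addition, we will assess intrinsic motivation, perceived ease of use, and perceived usefulness of each HIT". It gives no time point for either kind.

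**The concern.** The analysis text promises two readings and the schedule provides for one. Two separate sections send staff to Table 2 for timing, so the table is what they could be expected to follow. The missing reading is the one that cannot be collected late: once a Veteran has worked through modules, a pre-use expectation can no longer be measured.

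At stake is what the primary Phase 3 analysis can say. Module use accrues over weeks 1 to 7. A belief measured only at week 7 may reflect how use went as much as it explains it. A participant who does not complete the week-7 survey also contributes no belief score at all, even if the module count is known.

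**Working it through.** The plan gives no figure to reproduce here. The check compares the two texts and counts readings.

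**Readings stated and readings scheduled**

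| Instrument | Section 3.5, Aim 3a | Table 2: baseline | midpoint | week 7 | 1 month |
|---|---|---|---|---|---|
| Usability Survey (acceptability subscales) | pre and post | 0 | 0 | 1 | 0 |
| SUS | pre and post | 0 | 0 | 1 | 0 |

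**Is this an artefact of a broken table?** No. Other rows of Table 2 fall in sensible columns: Demographics at baseline only; MEAQ at baseline, week 7 and 1 month. In any case, a single mark cannot provide both a pre and a post reading, whichever column it sits in.

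**Does other text supply the missing reading?**
- Section 3.3 places a full battery of primary outcome and process measures at 3 and 7 weeks. Neither time is before use, and Table 2 has no midpoint mark for these two instruments.
- The staff calls at weeks 3 and 6 touch on usability problems, but they are brief safety assessments. They are not these scales, and they are not before use.
- The Phase 3 instrument descriptions in section 3.4 give no baseline reading.

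**Count if Table 2 is followed.** Section 3.5 plans n = 20 in the VACT-CP arm. Participants with a pre-intervention Usability Survey score: 0 of 20. The SUS is left out of this count of lost data, because it rates a system that the respondent has already used.

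**Effect on the planned analysis.** Section 3.5 specifies descriptive statistics, Cronbach's alphas, Pearson correlations and regression models. None uses a change from pre to post, so all can be computed from week-7 data. With both sides of each correlation fixed only at or after the end of use, the order of belief and use cannot be established.

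**The case against.** The strongest reply is that nothing planned fails. Both Aim 3a hypotheses are correlational, the Phase 3 objective is to explore relationships, no change score is specified, and no hypothesis claims that beliefs come before use. That stands, and it limits the harm. It does not settle which timing applies, and it does not restore a reading that the primary analysis text states.

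A second reply is that Table 2 may simply be incomplete. The PCL-5 and the Columbia scale appear in the text but not in the table, so the table does not list everything. This makes the consequence conditional on staff following Table 2. It also shows why the timing should be stated once, without conflict.

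A third reply is that the pre-intervention wording may itself be the mistake, at least for the SUS. For the SUS that is probably right. For the Usability Survey the documents do not show which text was intended.

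A reader might go further than the documents allow in three ways:
- *That the antecedent subscales are also promised before the intervention.* They are not. Section 3.5 mentions them in the preceding sentence, which gives no time point. The pre-and-post statement covers acceptability features only.
- *That a pre-use SUS score is lost data.* A score that needs exposure could not sensibly be taken, so for the SUS the fault is one of wording.
- *That the baseline battery holds nothing relevant.* Section 3.5's own example of an antecedent is health care need. The baseline VR-36, PHQ-9, BPI and record review bear on it, although they do not measure beliefs about the system.

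**Conclusion.** The inconsistency is real, lies within current text, and is not resolved elsewhere in the documents. If Table 2 is followed, the pre-intervention Usability Survey reading stated for the primary Aim 3a is collected for 0 of 20 VACT-CP participants and cannot be recovered. Aim 3a then yields post-use associations among week-7 responders, with no evidence on the order of beliefs and use.

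This rests on one assumption: that staff follow Table 2 rather than the analysis text. A reader might infer that the Aim 3a analysis is invalid or cannot be run. The documents do not support that, since every planned statistic can be computed and the hypotheses as worded can be addressed. The point should be fixed before enrolment because it touches the primary analysis, is irrecoverable afterwards and is cheap to correct. It does not undermine the pilot as a whole.

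**What to change.** Reconcile section 3.5 (Aim 3a) and Table 2 before enrolment.

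**If a baseline reading is intended:**
1. Add a baseline mark in Table 2 for the Usability Survey, with the acceptability subscales worded as expectations. Phase 2 uses a retrospectively worded form after exposure, so state which wording applies at each time point.
2. Keep the week-7 reading.
3. Correlate the baseline scores with the number of modules completed (0-7). If the count comes from website records, this analysis does not depend on return of the week-7 survey.
4. Remove the pre-intervention reading for the SUS from section 3.5.

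As a separate, low-cost improvement, take the antecedent subscales at the same baseline reading. Section 3.4 proposes that these conditions influence acceptance and use, so they are better measured before use. Taking only these would not resolve the inconsistency.

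**Cost.** The plan says: "The usability survey should take the average user about 5-7 minutes". That is the upper limit per participant, with no extra visit. For the VACT-CP arm, 20 × 5 to 20 × 7 = 100 to 140 minutes in total. If baseline questionnaires come before allocation, all 40 would answer: 40 × 5 to 40 × 7 = 200 to 280 minutes, and the Table 2 footnote would need a matching change. Sections 3.4 and 4.5.2b give about 2 hours for baseline. No times are given for the SCID-5 or the Columbia scale, so whether the addition fits cannot be worked out from the documents. If it does not fit, update both sections.

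**If no baseline reading is intended:** delete the pre-intervention timing from section 3.5 and report Aim 3a as concurrent, post-use associations among week-7 responders. This costs wording only.
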